3. TRIAL OBJECTIVES AND ENDPOINTS

3.1. Objectives

3.1.1. Primary and Key Secondary Objectives

- **Primary:** To demonstrate that elacestrant compared with the SOC options of either fulvestrant or an AI is superior in prolonging PFS based on a blinded Imaging Review Committee (IRC) assessment in post-menopausal women and men with ER+/HER2-mBC, either in subjects with ESR1 mutations (ESR1-mut subjects) or in all subjects which includes subjects without detectable ESR1 mutations (ESR1-mut-nd)
- **Key Secondary:**
 - To compare overall survival (OS) between treatment groups in ESR1-mut subjects
 - To compare OS between treatment groups in all subjects (ESR1-mut and ESR1-mut-nd)

3.1.2. Other Secondary Objectives

The following secondary objectives will be assessed for ESR1-mut-nd subjects:

- To compare PFS based on blinded IRC assessment between treatment groups
- To compare OS between treatment groups

The following secondary objectives will be assessed for ESR1-mut subjects, ESR1-mut-nd subjects, and all subjects (ESR-mut and ESR1-mut-nd)

- To compare PFS based on local Investigator assessment between treatment groups
- To compare ORRs based on blinded IRC assessment between treatment groups
- To compare DoR based on blinded IRC assessment between treatment groups
- To compare CBR based on blinded IRC assessment between treatment groups
- To compare ORR based on local Investigator assessment between treatment groups
- To compare DoR based on local Investigator assessment between treatment groups
- To compare CBR based on local Investigator assessment between treatment groups

The following other secondary objectives will be assessed for ESR1-mut and all subjects (ESR1-mut and ESR1-mut-nd):

- To compare the safety and tolerability between treatment groups
- To assess the PK of elacestrant
- To describe the changes in Patient Reported Outcomes (PROs) and Health-Related Quality of Life (HRQOL) and the changes in PROs/HRQOL between treatment groups

3.1.3. Exploratory Objectives

The following exploratory objectives will be assessed in ESR1-mut subjects, ESR1-mut-nd subjects, and all subjects (ESR1-mut and ESR1-mut-nd):

- To determine the difference in time to chemotherapy (TTC) between treatment groups
- To evaluate alterations in ctDNA relevant to ER+ breast cancer and the CDK4/6 pathway and to explore the relationship between these findings and clinical response
- To characterize alterations in tumor-specific genes, proteins, and RNAs related to oncogenic pathways and proliferation and cell cycle markers in tumor tissues and to explore the relationship between these findings and clinical response

3.2. Endpoints

3.2.1. Primary and Key Secondary Endpoints

3.2.1.1. Primary Endpoints

The primary endpoints of this study are as follows:

- IRC-assessed PFS in ESR1-mut subjects
- IRC-assessed PFS in all subjects (ESR1-mut and ESR1-mut-nd)

IRC-assessed PFS is defined as the length of time from randomization until the date of objective disease progression per RECIST v1.1 ([Appendix 1](#)) as assessed by the blinded IRC or death from any cause.

3.2.1.2. Key Secondary Endpoints

The key secondary endpoints are as follows:

- OS in ESR1-mut subjects
- OS in all subjects (ESR1-mut and ESR1-mut-nd)

OS is defined as the length of time from randomization until the date of death from any cause.

3.2.2. Other Secondary Endpoints

The following endpoints will be analyzed for ESR1-mut-nd subjects:

- IRC-assessed PFS
- OS

The following endpoints will be analyzed for ESR1-mut, ESR1-mut-nd, and all subjects (ESR1-mut and ESR1-mut-nd):

- Local Investigator-assessed PFS, defined as the length of time from randomization until the date of objective disease progression per RECIST v1.1 as assessed by local Investigators or death from any cause

- IRC-assessed ORR, defined as the percentage of subjects with measurable disease who have achieved either a confirmed complete response (CR) or PR per RECIST v1.1 based on blinded IRC assessment
- IRC-assessed DoR, defined as the duration of time from the date when criteria are met for either a CR or PR, per RECIST v1.1, until the first date that recurrent or progressive disease (PD) is objectively documented based on blinded IRC assessment
- IRC-assessed CBR, defined as the percentage of subjects who have achieved either a confirmed CR or PR or stable disease (SD) at ≥ 24 weeks from randomization per RECIST v1.1 based on blinded IRC assessment
- Local Investigator-assessed ORR
- Local Investigator-assessed DoR
- Local Investigator-assessed CBR

The following endpoints will be assessed for ESR1-mut subjects and all subjects (ESR1-mut and ESR1-mut-nd):

- Safety and tolerability, assessed by AEs, SAEs, dose modifications, clinical laboratory parameters (ie, hematology, chemistry, and coagulation), ECGs, performance status, and vital signs
- PK, assessed by evaluation of elacestrant concentrations at pre-dose (pre-treatment) and 4 hours post-dose on Cycle 1 Day 1 (C1D1), pre-dose (trough concentration [C_{trough}]) and 4 hours post-dose on C1D15, and pre-dose (C_{trough}) on C2D1
- PRO endpoints, assessed using the HRQOL scales EuroQOL 5 Dimension 5 Level (EQ-5D-5L), European Organization for Research and Treatment of Cancer (EORTC) Quality of Life Questionnaire-Core 30 (QLQ-C30), and PRO Version of the Common Terminology Criteria for Adverse Events (PRO-CTCAE)

3.2.3. Exploratory Endpoints

The following exploratory endpoints will be assessed in ESR1-mut subjects, ESR1 mut-nd subjects, and all subjects (ESR1-mut and ESR1-mut-nd):

- TTC, defined as the number of days from randomization to initiation of chemotherapy
- Alterations in ctDNA relevant to ER+ breast cancer and the CDK4/6 pathway and the relationship between these findings and clinical response
- Alterations in tumor-specific genes, proteins, and RNAs related to oncogenic pathways and proliferation and cell cycle markers in tumor tissue and the relationship between these findings and clinical response

4. INVESTIGATIONAL PLAN

4.1. Overall Study Design

This is an international, multicenter, randomized, open-label, active-controlled, event-driven, Phase 3 clinical study comparing the efficacy and safety of elacestrant to the SOC options of either fulvestrant or an AI in post-menopausal women and men with ER+/HER2- mBC whose disease has relapsed or progressed on at least 1 and no more than 2 prior lines of endocrine therapy for mBC, which must have included CDK4/6i therapy in combination with fulvestrant or an AI. Subjects must have received no more than 1 line of cytotoxic chemotherapy in mBC. Endocrine monotherapy with 1 of the SOC drugs (fulvestrant, anastrozole, letrozole, exemestane) must be an appropriate treatment option for subjects enrolled in this study. The primary endpoints of IRC-assessed PFS will be analyzed in ESR1-mut subjects and in all subjects (ESR1-mut and ESR1-mut-nd) using the Hochberg procedure to adjust for the multiplicity of the primary endpoints. A schematic of the study design is provided in [Figure 4](#).

Subjects who meet all eligibility criteria will be enrolled into the active treatment phase of the study. During this phase of the study, subjects will receive study drug as defined in the protocol and will undergo the protocol-defined safety, efficacy, and exploratory assessments. Subjects will continue to receive treatment until the following: disease progression, a clinically significant AE, significant study noncompliance, the subject is unable to receive study treatment for > 14 consecutive days, treatment discontinuation in the best interest of the subject, or subject refuses treatment as defined in [Section 5.3.1](#) requires subject withdrawal.

Subjects who discontinue the active treatment phase due to disease progression will enter a follow-up phase during which survival data and the start date and regimen name of the first new anti-cancer therapy will be collected. For subjects who discontinue treatment for reasons other than disease progression, death, consent withdrawal, toxicity, or loss to follow-up and who do not begin new anti-cancer therapy, tumor assessments will continue until disease progression or the first new anti-cancer therapy is initiated. At that time, subjects will discontinue tumor assessments and continue to be monitored for survival data and the initiation of the first new anti-cancer therapy.

[figure not shown]
This is an open-label study and study subjects and Investigators will not be blinded to treatment assignment. However, to minimize bias in study conduct, RADIUS personnel performing statistical analyses, including biostatisticians, and programmers, will be blinded to treatment assignment until after database lock. Clinical Research Organization (CRO) study team members and select RADIUS team members will not be blinded to an individual subject's treatment assignment during the conduct of the study but will be blinded to aggregated data by treatment assignment until after database lock.

An independent IRC, blinded to subjects' treatment assignments, will review radiographic images and clinical information collected on study to determine the protocol-defined endpoints of disease response and progression.

Safety and efficacy data (PFS by IRC and local Investigator and OS) will be reviewed at prespecified intervals by an Independent Data Monitoring Committee (IDMC). An unblinded statistician at the CRO will perform all analyses in preparation for the IDMC evaluations.

A survival analysis will be performed at the same time as the final PFS analysis when approximately 160 PFS events (objective disease progression assessed by the blinded IRC or death) among the ESR1-mut subjects and 340 PFS events among all subjects (ESR1-mut and ESR1-mut-nd) have occurred and again when approximately 50% of subjects have died at which time the study will be complete.

Figure 4: Study Design

AI = aromatase inhibitor; EOT = end of treatment; ER+ = estrogen-receptor positive; ESR1 = estrogen receptor gene 1; HER2- = human epidermal growth factor receptor 2 negative; PD = progressive disease; SOC = standard of care

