2.2.2.5.4. Combined Safety from Studies RAD1901-005 and RAD1901-106

Safety data were combined for subjects enrolled in the 2 Phase 1 studies of elacestrant in postmenopausal women with mBC and are presented in Table 5 and Table 6 for subjects treated at the RP2D of 400 mg QD. Data are presented separately for subjects treated with the capsule formulation and the tablet formulation. Two subjects in study RAD1901-106, and 3 subjects in study RAD1901-005, initially received capsules and were then switched to tablets; these 5 subjects are included in the capsule group in the tables below.

Most subjects receiving either formulation experienced TEAEs and treatment-related TEAEs (Table 5). The incidence of subjects experiencing TEAEs leading to dose interruption and Grade 3 or 4 TEAEs were similar between the 2 formulations, while the incidence of SAEs was higher in subjects with tablets as compared to those with capsules. There were no treatment-related deaths.

Table 5: Overall Summary of Adverse Events in Subjects with Breast Cancer using Combined Data from RAD1901-106 and RAD1901-005 (ITT Population)

Adverse Event Category	Elacestrant 400 mg capsules (N=42) ^a n (%)	Elacestrant 400 mg tablets (N=24) n (%)	Overall (N=66) ^a n (%)
TEAEs	42 (100)	22 (91.7)	64 (97.0)
Treatment-Related TEAEs	40 (95.2)	19 (79.2)	59 (89.4)
Serious TEAEs	8 (19.0)	8 (33.3)	16 (24.2)
Treatment-Related Serious TEAEs	2 (4.8)	1 (4.2)	3 (4.5)
TEAEs Leading to Dose Interruption	13 (31.0)	8 (33.3)	21 (31.8)
Treatment-Related TEAEs Leading to Dose Interruption	9 (21.4)	1 (4.2)	10 (15.2)
TEAEs at Grade 3 or 4 ^b	16 (38.1)	10 (41.7)	26 (39.4)
Treatment-Related TEAEs at Grade 3 or 4	9 (21.4)	1 (4.2)	10 (15.2)
TEAEs Leading to Death	1 (2.4)	1 (4.2)	2 (3.0)
Treatment-Related TEAEs Leading to Death	0	0	0
TEAEs Leading to Study Medication Discontinuation	8 (19.0)	1 (4.2)	9 (13.6)
Treatment-Related TEAEs Leading to Study Medication Discontinuation	7 (16.7)	0	7 (10.6)

Treatment-Emergent Adverse Events (TEAEs) are those events which started on or after the first dose of study medication.

a Eight patients initiated treatment at 200 mg for 14 days.

b Severity grad based upon CTCAE version 5.0

Study RAD1901-106 database lock date: November 27, 2018.

Study RAD1901-005 database lock date: December 20, 2019.

Source: [SRT Table 2.1](#)

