4.4. Disease Progression and Tumor Assessments

Tumor assessments will be performed every 8 weeks (\pm 7 days) from the date of randomization during the active treatment phase of the study. Subjects with bone lesions identified by radionuclide bone scan or whole body magnetic resonance imaging (MRI) at baseline (during Screening) will have repeat bone scans or whole body MRI (using the same modality as used

during Screening) performed every 24 weeks (± 7 days) from the date of randomization and at time of confirmation of a CR. All assessments will be performed as scheduled at the required intervals according to the Schedule of Events ([Appendix 2](#)), regardless of any dosing delay to prevent the introduction of bias into the assessment of efficacy.

Tumor assessments will be performed until radiographically- and/or clinically-documented (ie, for photographed or palpable lesions) disease progression as per RECIST v1.1, initiation of new anti-cancer therapy, or discontinuation from overall study participation ([Section 7.4](#)), whichever occurs first.

Subjects who discontinue study treatment for reasons other than radiographically- and/or clinically- (ie, for photographed or palpable lesions) documented disease progression, per RECIST v1.1, will continue to have tumor assessments performed every 8 weeks (± 7 days) in the follow-up period, and bone scans or whole body MRI (as applicable) as clinically indicated and/or every 24 weeks (± 7 days) until RECIST-defined disease progression, initiation of the first new anti-cancer therapy, or discontinuation from overall study participation (eg, death, withdrawal of consent, lost to follow-up), whichever occurs first.

Subjects no longer undergoing tumor evaluations will continue to be monitored every 8 weeks for survival data and the initiation of the first new anti-cancer therapy.

The follow-up period will conclude at the time of the final OS analysis when approximately 50% of subjects in the study have died.

Efficacy analyses will be performed using tumor assessments made by the blinded IRC as the primary data source. Analyses of endpoints based on local Investigator assessment will also be performed as supportive analyses.

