7.4. Tumor Assessments

7.4.1. Overview

- Tumor assessments will be performed following the RECIST v1.1 criteria ([Appendix 1](#))
- Tumor assessments will be performed at Screening and every 8 weeks, (± 7 days) from the date of randomization during the active treatment phase of the study (and in the follow-up period for subjects who have discontinued study drug for reasons other than PD [clinical PD or PD confirmed by RECIST] and have not yet started new anti-cancer therapy)
 - For Screening assessments, radiographic assessments obtained per the subject's SOC prior to signing consent for the study do not need to be repeated and are acceptable to use as Screening evaluations, if (1) they were obtained within 28 days before randomization (with the exception of radionuclide bone scans/whole body MRI scans which must be within 12 weeks of randomization and brain computed tomography (CT) or MRI scans which must be within 6 weeks of randomization); (2) they were performed using the method requirements outlined in RECIST v1.1 and they meet all imaging requirements as outlined herein and the Bioclinica Site Manual; (3) the same technique/modality can be used to follow identified lesions throughout the trial for a given subject; and (4) appropriate documentation indicating that these radiographic tumor assessments were performed as SOC is available in the subject's source notes
 - All assessments performed during the active treatment phase of the study will be performed as scheduled at the required intervals according to the Schedule of Events, regardless of any dosing delay, to prevent the introduction of bias into the assessment of efficacy ([Table 18](#) in [Appendix 2](#))
- All tumor assessments, including those performed during Screening to assess eligibility and baseline tumor measurements, will be collected and sent to a core imaging vendor for blinded IRC analysis. Instructions on collection and transmission/shipping will be provided in the Bioclinica Site Manual

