8.5. Post-Treatment Follow-Up

Post-treatment Follow-Up is to occur every 8 weeks (± 7 days) (see [Appendix 2](#)).

For subjects who discontinue study treatment because of objective disease progression or clinical progression in the absence of progression by RECIST, survival data will be collected every 8 weeks (± 7 days), calculated from the last dose of study treatment, for the duration of the study. The start date and regimen name of the first new anti-cancer therapy will also be collected. Telephone contact is acceptable.

Note: Subjects who discontinue treatment for reasons other than disease progression and who do not begin a new anti-cancer therapy will continue to have tumor assessments every 8 weeks (± 7 days) from the date of randomization, and bone scans or whole body MRI every 24 weeks (± 7 days) as indicated, until disease progression is documented, or new anti-cancer therapy is initiated, at which time they will continue to be monitored every 8 weeks (± 7 days) for first new anti-cancer therapy and survival for the duration of the study.

At any time after 30 days from the last dose of study treatment, the Investigator may report any SAE that he/she believes is related to study treatment.

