- f. For subjects who discontinue study treatment due to objective disease progression, survival data and start date and regimen name of the first new anti-cancer therapy should be collected every 8 weeks (± 7 days) calculated from the last dose of study drug for the duration of the study. For subjects who discontinue treatment for reasons other than disease progression, and who do not begin new anti-cancer therapy, tumor assessments will continue every 8 weeks (± 7 days, from the date of randomization), and for subjects with bone lesions at baseline radionuclide bone scan or whole body MRI will be performed every 24 weeks (± 7 days), as indicated, until disease progression is documented, or new anti-cancer therapy is initiated; at that time, they will continue to be monitored every 8 weeks for survival and first new anti-cancer therapy information for the duration of the study.
- g. Informed consent must be obtained prior to any protocol-required assessments (except for certain imaging assessments if they meet the criteria defined in [Table 20](#)).
- h. ER and HER2 status must be confirmed per local laboratory testing.
- i. Prior anti-cancer therapy, including drug names, treatment start/end date, dose, setting (neoadjuvant, adjuvant, or recurrent/metastatic line of therapy), best response, date of disease progression, and reason for treatment discontinuation, are to be recorded.

- j. Randomization is to occur after eligibility is determined by the study site and confirmed by the Medical Monitor. The planned first dose of C1D1 is to start within 1 day after randomization; randomization may occur on D-1 or on D1. Note: there is no Day 0 in this study. C1D1 is the date of first dose of study drug.
- k. PRO questionnaires are to be completed by the subject using the electronic tablet provided while in clinic (cannot be taken home) at the beginning of the study visit and prior to any other assessments or significant interactions with site staff. PRO questionnaires will be performed on C1D1, C1D15, C2D1, and D1 of each subsequent cycle through C4, then D1 of every other cycle thereafter starting with C6 (ie, C2, C3, C4, C6, C8, C10, etc), at EOT, and at the Safety Follow-Up visit (unless this visit is performed via phone contact). Note: If a certified translation for any PRO questionnaire is not available for a subject, that specific PRO assessment can be omitted, but the reason must be documented.

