- s. Chemistry includes BUN or urea, creatinine, sodium, potassium, chloride, bicarbonate, calcium, phosphorous, magnesium, albumin, total protein, total bilirubin (direct and indirect if total is > ULN), alkaline phosphatase, ALT, AST, glucose and lipid panel (total cholesterol, LDL, HDL, and triglycerides). If possible, the glucose and lipid panel should be performed with the subject in a fasting state. If performed > 7 days prior to C1D1, must be repeated and eligibility criteria must still be met.
- t. Hemoglobin A1c is to be measured at Screening and EOT.
- u. Coagulation tests include PT or INR (per the sites's standards), aPTT (PTT is allowed if aPTT is not available), and fibrinogen. INR is required at Screening. If performed > 7 days prior to C1D1, must be repeated and eligibility criteria must still be met.
- v. Diagnostic CT for tumor assessment may be used even if acquired during PET/CT hybrid imaging providing the CT images are of sufficient quality. Screening tumor assessments must be performed during the Screening period (Day -28 through Day -1) as noted in [Table 20](#). For subjects who achieve a CR or PR, a confirmation scan must be repeated at least 4 weeks after the first documented response. Subjects with history of stable brain metastases should have brain CT or MRI imaging in parallel with systemic imaging for evaluation of non-target lesions in the brain; brain CT or MRI scans are not otherwise required as part of standard imaging. Color photographs must be taken of any skin lesions that will be followed as either target or non-target lesions. Tumor evaluation will be performed at EOT unless an evaluation has been performed within the preceding 28 days or disease progression has already been documented per RECIST v1.1. See [Table 20](#). For subjects who discontinue treatment for reasons other than disease progression (clinical PD or PD by

- RECIST criteria), and who do not begin new anti-cancer therapy, tumor assessments will continue every 8 weeks from the date of randomization until documentation of progression or start of new anti-cancer treatment; for these subjects, additional assessments do not need to be performed at the EOT visit.
- w. To be completed within 28 days prior to randomization.

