^c Subjects who have already demonstrated objective disease progression as per RECIST v1.1 do not need to have scans repeated at the end of treatment visit or during the post-treatment follow-up. For subjects who do not have documented objective disease progression at time of study treatment discontinuation, tumor assessment will continue to be performed every 8 weeks (± 7 days), and bone scans or whole body MRI (as applicable) every 24 weeks (± 7 days) until radiographically and/or clinically confirmed objective disease progression, initiation of first new anti-cancer therapy, or discontinuation of subject from overall study participation (eg, death, subject's request, lost to follow-up).

^d CT scans, including brain CT scan if applicable, should be performed with contrast agents unless contraindicated for medical reasons. If IV contrast is medically contraindicated, the imaging modality to be used to follow the disease (either CT without contrast or MRI) should be the modality which best evaluates the disease, and the choice should be determined by the Investigator in conjunction with the local radiologist per RECIST v1.1. MRI of the abdomen and pelvis can be substituted for CT if MRI adequately depicts the disease. However, MRI of the chest should not be substituted for CT of chest even if IV contrast is contraindicated. In such cases, CT will be performed without contrast. MRI of the chest should only be performed in extenuating circumstances. If MRI is used to follow bone lesion(s), it must be performed a few days before any treatment that may affect bone marrow cellularity (eg, G-CSF). Diagnostic CT for tumor assessment may be used even if acquired during PET/CT hybrid imaging providing the CT images are of sufficient quality.

^e Radiographic assessments obtained per the subject's standard of care prior to randomization into the study do not need to be repeated and are acceptable to use as baseline evaluations if: (1) obtained within 28 days before randomization, (2) they were performed using the method requirements outlined in RECIST v1.1 (3) the same technique/modality can be used to follow identified lesions throughout the trial for a given subject, and (4) appropriate documentation indicating that these radiographic tumor assessments were performed as standard of care is available in the subject's source notes.

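### Protocol 4.1 leaves subjects who stop treatment for toxicity out of continued tumor imaging, while every other imaging passage keeps them in; the effect on PFS is probably small and its direction is unknown

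*Protocol*

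**What the plan says.** Protocol 4.1 (Overall Study Design) continues tumor assessments after a treatment stop for "reasons other than disease progression, death, consent withdrawal, toxicity, or loss to follow-up and who do not begin new anti-cancer therapy". Toxicity therefore stands in one list with progression, death, withdrawn consent and loss to follow-up. The sentence does not order scans to stop; it leaves these subjects out of the group whose scans continue.

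The other imaging passages have no such exception:

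- Protocol 4.4: "Subjects who discontinue study treatment for reasons other than radiographically- and/or clinically- (ie, for photographed or palpable lesions) documented disease progression" stay on the 8-week schedule.
- Protocol 7.4.1: assessments run "in the follow-up period for subjects who have discontinued study drug for reasons other than PD" and have not started new therapy.
- Protocol 8.5: "Subjects who discontinue treatment for reasons other than disease progression and who do not begin a new anti-cancer therapy will continue to have tumor assessments".
- Table 18 footnote f: "For subjects who discontinue treatment for reasons other than disease progression, and who do not begin new anti-cancer therapy, tumor assessments will continue".
- Table 18 footnote v: "tumor assessments will continue every 8 weeks from the date of randomization until documentation of progression or start of new anti-cancer treatment".
- Table 20 footnote c: "For subjects who do not have documented objective disease progression at time of study treatment discontinuation, tumor assessment will continue to be performed".

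SAP Table 1 reproduces footnotes f and v. These passages differ among themselves on clinical progression without RECIST progression, which is a separate matter. On toxicity they agree. All of them, 4.1 included, end imaging at the first new anti-cancer therapy.

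SAP 4.7.1.1 defines PFS regardless of withdrawal from randomized therapy and censors at new systemic therapy. Without progression or death, the subject is censored at the last adequate assessment. Progression or death after two or more missed assessments, set at 18 weeks since the previous assessment, is also censored.

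**The concern.** Toxicity does not belong with the other reasons in the 4.1 list. Progression supplies the event; death, withdrawn consent and loss to follow-up make further imaging impossible. A subject stopped for an adverse event can still be imaged and is still at risk of progression.

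If a site follows 4.1, that subject's later progression is never seen and becomes a censoring at the last scan. Stopping for toxicity depends on treatment and may be related to prognosis, so the censoring could differ by arm and be informative for the primary endpoint. Sensitivity Analyses 1 and 2 (SAP 4.7.1.3) reinstate only events that were recorded after missed assessments. SAP Table 2 has no row for imaging ended at a toxicity stop, and the check of censoring patterns in SAP 4.7.2.2 covers OS only.

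**Working it through.** **1. The passages side by side.** Take a subject stopped for an adverse event, alive, consenting, without progression and on no new therapy. Under 4.1 this subject is outside continued imaging. Under 4.4, 7.4.1, 8.5, Table 18 footnotes f and v and Table 20 footnote c the subject is inside it. Both cannot hold.

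**2. The plan's own power.** With 1:1 allocation and two-sided alpha 2.5%, power = Φ(√(D/4)·|ln HR| − 2.241).
- ESR1-mut: √40 × 0.494 − 2.241 = 0.885, giving 81.2% (plan: 80% at 160 events, HR 0.610).
- All subjects: √85 × 0.405 − 2.241 = 1.492, giving 93.2% (plan: 92% at 340 events, HR 0.667).

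Both reproduce to within 2 points.

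**3. Subjects affected.** Protocol Table 5 ("TEAEs Leading to Study Medication Discontinuation") gives 1/24 = 4.2% (tablets), 9/66 = 13.6% (pooled) and 8/42 = 19.0% (capsules). SAP 4.1 gives 478 enrolled, so about 239 per arm. 239 × 0.042, 0.136 and 0.190 = 10, 33 and 45 elacestrant subjects. No SOC rate is given.

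**4. Upper bound on lost events.** Assume that no toxicity stopper ever starts new therapy. Simulation inputs: 239 per arm, HR 0.667, SOC median 5.3 months (stated only for ESR1-mut subjects, assumed here for all), cutoff at month 31, stops in roughly the first 4 months, SOC stops 2-4%. About 10, 25-32 or 35-42 events are lost, out of about 410 accruing by month 31 in this model. These models lose every PFS event after the stop, including deaths that the 18-week rule would keep.

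**5. Allowing for new therapy.** Imaging ends at new therapy under either wording, so 4.1 costs only the events that fall between the stop and new therapy. By hand, for the elacestrant arm:
- Median PFS is 5.3/0.667 = 7.95 months. With a stop at month 2, the share still event-free is 2^(−2/7.95) = 0.84.
- With median m months to new therapy, the share with an event first is m/(m + 7.95): 0.11 at m = 1 and 0.33 at m = 4.
- For 33 subjects: 33 × 0.84 × 0.11 ≈ 3 and 33 × 0.84 × 0.33 ≈ 9 events.
- If stoppers have twice the hazard, the median is 3.97 months and the factors become 0.70 with 0.20 and 0.50: 33 × 0.70 × 0.20 ≈ 5 and 33 × 0.70 × 0.50 ≈ 12.

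Over all simulation settings tried, including SOC stops, the loss is about 1-6, 2-17 or 3-23 events at the three rates.

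**6. Hazard ratio.** All subjects, 13.6% elacestrant stops, no SOC stops and no new therapy (the unfavorable extreme):
- equal hazard: 0.669 to 0.669;
- stoppers' hazard ×1.5: 0.701 to 0.676;
- stoppers' hazard ×2: 0.721 to 0.682.

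With new therapy at a median of 1-4 months the shift is about 0 to 0.02, and at most 0.03 at the capsule rate. Equal 4.2% rates in both arms give no material shift. With 8% SOC against 4.2% elacestrant the shift reverses and stays below 0.01.

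**7. Power.** Fixed calendar cutoff, 47% of events assumed in the elacestrant arm, every stopper's event lost, no SOC stops. ESR1-mut: 160 × 0.47 × rate = 3, 10 and 14 events lost, power 80.3%, 78.3% and 77.1%. All subjects: 340 × 0.47 × rate = 7, 22 and 30 lost, power 92.7%, 91.5% and 90.7%.

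**The case against.** The strongest reply is that 4.1 is a design overview and is silent by exception, while the passages that sites work from agree with one another. Protocol 5.3.1 also sends a subject who stops treatment to follow-up as set out in the Schedule of Events, which continues imaging. Nothing in the documents shows that any site followed 4.1. This stands as an argument about likelihood; it does not remove the contradiction.

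Four stronger readings are tempting, and the documents do not support them.

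- *The conflict biases PFS toward elacestrant.* This needs more toxicity stops on elacestrant than on SOC and a worse prognosis among the stoppers. The documents give neither. This trial uses tablets, for which the rate is 1/24 (exact 95% interval 0.1% to 21%); 8 of the 9 pooled stops were in capsule subjects.
- *Dozens of PFS events would be lost.* That assumes nobody starts new therapy after a toxicity stop. Events after new therapy are censored under either wording.
- *Every later death is lost as well.* A death within the 18-week window still counts, and recorded later deaths return in Sensitivity Analyses 1 and 2. Only progression that was never imaged is beyond recovery.
- *The trial loses its power.* It is event-driven, so lost events mainly delay the cutoff.

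**Conclusion.** The contradiction holds. Protocol 4.1 conflicts with six other protocol passages, with two footnotes repeated in the SAP, and with a PFS definition that presupposes follow-up after a treatment stop. Followed as written, 4.1 would turn some primary-endpoint events into censorings at a stop that may depend on treatment.

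The size is uncertain and probably small: about 1-6 events at the tablet rate, 2-17 at the pooled rate and 3-23 at the capsule rate, with a hazard-ratio shift between about zero and 0.02 (0.03 at most at the capsule rate). These figures assume that sites follow 4.1, that new therapy starts a median of 1-4 months after the stop, and, for any shift at all, that toxicity stoppers do worse than others. Without an SOC stop rate the direction cannot be stated. The lasting concern is arm-dependent censoring rather than power. This is a consistency correction affecting the primary endpoint, not a fault that should hold up the trial or its analysis.

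**What to change.** Reconcile Protocol 4.1 with 4.4, 7.4.1, 8.5, Table 18 footnotes f and v and Table 20 footnote c by removing toxicity from the imaging exception list, so that PFS ascertainment matches the SAP definition. This concerns endpoint imaging only, not when treatment stops. Send sites a short clarification. Before the PFS analysis, list by arm the subjects who stopped for toxicity and whose scans ended without progression, death or new therapy; that shows whether the conflict had any effect and in which arm.

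The cost is one word, a site memo and a listing, plus a few continued scans that the Schedule of Events already requires. SAP 4.1 reports enrollment complete, so the change helps only subjects still in follow-up, and scans not taken cannot be recovered. It is best done before data cut-off.
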